International multicenter double-blind placebo-controlled randomized parallel-group clinical trial of Anaferon for children efficacy in prevention of influenza and other acute respiratory viral infections in children during the peaks of seasonal morbidity

Phase IV

Sponsor

OOO «NPF «MATERIA MEDICA HOLDING»

Protocol numberMMH-AD-008Version date:August 23, 2018ClinicalTrials.gov Id:NCT03301155

Protocol Summary

This document represents the protocol summary for the study on human subjects. The study will be carried out in accordance with ICH GCP, National Standard of the Russian Federation GOST 52379-2005 "Good Clinical Practice", Helsinki Declaration of World Medical Association, relevant requirements of the regulatory authorities as well as the study procedures.

Title of Study

International multicenter double-blind placebo-controlled randomized parallel-group clinical trial of Anaferon for children efficacy in prevention of influenza and other acute respiratory viral infections in children during the peaks of seasonal morbidity.

Phase: IV

Sponsor: OOO "NPF "Materia Medica Holding", Moscow, Russia *Protocol No.* MMH-AD-008

Objective of the study

• To obtain additional data on the efficacy and safety of 12-week course of therapy with Anaferon for children for prevention of influenza and other acute respiratory viral infections in children during the peaks of seasonal morbidity.

Endpoints

Primary endpoint

1. Time from taking the first dose of the study drug to the onset of influenza/ARVI symptoms.

Secondary endpoints

- 1. Percentage of children not falling ill with influenza or another ARVI during 4, 8, or 12week preventive course (based on medical records).
- 2. Percentage of children with the symptoms of a respiratory or ear-nose-throat bacterial infection requiring antibacterial therapy within 12-week preventive course (based on medical records).
- 3. Percentage of children hospitalized for influenza/ARVI or their complications within 12week preventive course (based on medical records).

Safety assessment

• Presence and type of adverse events, their severity, relation to investigational drug, outcomes.

Study design

Design: an international, multicenter, double-blind, placebo-controlled, randomized study in parallel groups.

The study will enroll children of both gender from 1 month to 6 years old. Children can participate in the study regardless of the frequency of previous ARVI. A potential study participant should not be in the incubation (if known), prodromal, acute /subacute periods of any infectious disease (except for the recovery period). Schedule for enrollment of participants: during the period of a seasonal rise in influenza/ARVI incidence in the Russian Federation and the Republic of Uzbekistan. Screening and randomization of participants will be subject to availability of official information on the incidence of influenza/ARVI in the relevant study region.

The doctor makes the first visit to the participant in the medical center or at home. After parent/adoptive parent signs the information sheet (informed consent form), the doctor evaluates the possibility of the participant being included in the trial. If the child meets all the inclusion criteria and does not have all non-inclusion criteria, then he/she is included in the study, the doctor fills in the Clinical Research Form. At visit 1 (Day 1), the participant is randomized into one of two groups: the 1st group participants will take Anaferon for children according to the preventive regimen for 12 weeks; the 2nd group participants will take Placebo according to the regimen of Anaferon for 12 weeks.

In total, the study participant will be observed for 12 weeks (screening and randomization up to 1 day, preventive treatment for 12 weeks).

During the observation period at 4 (Visit 2), 8 (Visit 3), and 12 (Visit 4) weeks, three visits are planned.

Visits 2 (Week 4 ± 3 days) and 3 (Week 8 ± 3 days) are conducted in the form of a telephone survey of parents/adoptive parents about the participant's health status, presence/absence of symptoms of influenza/ARVI, possible use of antibacterial drugs and/or hospitalization during the course preventive therapy.

Visit 4 (Week 12 ± 3 days) is carried out at home or in a medical center; the doctor collects complaints, examines the participant, registers concomitant therapy, assesses the compliance of the therapy.

If in the period from 2 to 12 weeks a participant falls ill with influenza/ARVI¹, then he prematurely completes participation in the study (as having reached the primary endpoint). A participant is considered fallen ill with influenza/ARVI if the doctor identifies the following symptoms: febrile/subfebrile body temperature, presence at least one flu-like nonspecific symptom (decreased activity/impaired behavior/weakness; headache; chills) and at least one respiratory symptom (runny nose; nasal stuffiness; hoarseness/husky voice; sore throat; cough). In this case, the doctor makes an unscheduled visit (at home or in a medical center), which is final. During the visit, the doctor carries out the procedures of Visit 4. A nasopharyngeal swab is taken to identify the most common pathogens of influenza/ARVI².

If ARVI/influenza occurs within the first seven days from the onset of preventive therapy, the disease will not be recorded as an adverse event and will not be taken into account to evaluate the efficacy of the study drug, since an early manifestation of influenza/ARVI may indicate that the participant was included in the study when he/she was in the incubation period of an infectious disease.

During the study, concomitant therapy for underlying chronic conditions, as well as routine vaccination of the participant, are allowed, with the exception of the drugs indicated in the section "Prohibited Concomitant Treatment".

Inclusion and exclusion criteria

Inclusion criteria

- 1. Children of either gender aged from 1 month to 6 years old³.
- 2. The absence of clinical symptoms of any infectious disease, but not earlier than 14 days from its onset.
- 3. Seasonal rise in ARVI incidence, confirmed by official information.
- 4. An information sheet (Informed Consent form) for the subject participation in the clinical trial signed by one parent/adopter of the patient.

Exclusion criteria

 Acute or subacute period of infectious disease of any etiology (viral, bacterial, fungal, etc.) and localization (including upper and lower respiratory tract infection, meningitis, sepsis, otitis media, urinary tract infection, intestinal infection, etc.).

¹ The symptoms associated with teething or vaccination (post-vaccination reactions and complications) are not considered as manifestations of influenza/ARVI.

² PCR-based diagnosis with the AmpliSens Reagent Kit to identify the most common pathogens of ARVI and influenza, including (1) Influenza A virus; (2) Influenza B virus; (3) Influenza A (H1N1)pdm, similar to A/California/4/2009; (4) Human metapneumovirus; (5) Human respiratory syncytial virus; (6) Human rhinovirus; (7) Human adenovirus; (8) Human bocavirus; (9) Human parainfluenza virus 1; (10) Human parainfluenza virus 2; (11) Human parainfluenza virus 3; (12) Human parainfluenza virus 4; (13) Human coronavirus OC43; (14) Human coronavirus 229E; (15) Human coronavirus HKU1; (16) Human coronavirus NL63.

³ The study participants are aged 1 month to 6 years 11 months and 29 days.

- 2. History of (verified previously) or current suspected conditions such as:
 - primary or secondary immunodeficiency⁴;
 - bronchopulmonary dysplasia, primary ciliary dyskinesia, cystic fibrosis, other chronic pulmonary diseases;
 - malformations of the respiratory and ENT organs (ear, throat, mouth, tongue, larynx, trachea, neck and salivary and thyroid glands, etc.);
 - immunopathological diseases (including Marshall syndrome, Behcet's syndrome, Kawasaki disease, etc.);
 - hematological diseases (including agranulocytosis, leukemia);
 - oncologic conditions.
- 3. Exacerbated or decompensated of chronic diseases affecting the participant's ability to participate in the clinical trial.
- 4. Malabsorption syndrome, including congenital or acquired lactase or another disaccharide deficiency, galactosemia.
- 5. Allergy/intolerance to any component of the study drug.
- 6. Course administration of the drug products specified in the section 'Prohibited concomitant medications' within 2 weeks prior to enrollment.
- 7. Children whose parents/adopter parents will fail to comply with the observation requirements of the trial or with the intake regimen of the study drug, from the investigator's point of view,
- 8. Participation in other clinical trials within 3 month prior to enrollment in the study.
- 9. The patient's parent/adopter parent is a member of the research team of the investigational site directly involved in the study or a close relative of an investigator. Close relatives are defined as husband/wife, parents, children, brothers (sisters) regardless of whether they are biological or adopted.
- The patient's parent/adopter parent works for OOO "NPF "MATERIA MEDICA HOLDING" (i.e., the company's employee, part-time employee under contract or appointed official in charge of the trial, or their immediate family).

Discontinuation criteria

1. Failure or refusal of the child or his/her parents/adopters to comply with the protocol.

⁴ Primary and secondary immunodeficiencies, regardless of etiology, are characterized by persistent immunodeficiency. Transient immunomodulation do not represent immunodeficiency. Children with recurrent respiratory infections have transient immunomodulation. High rates of infectious diseases during the first years of life should not be considered as a pathology; this condition is not attributable to immunodeficiency and does not exhibit negative effect on immunity formation. Such subjects are eligible.

Subjects with immunodeficiency need complex therapy using the products forbidden within the study.

- 2. The necessity to use medications not permitted within the study.
- 3. An adverse event requiring discontinuation of the investigational product.
- 4. The desire of the child or parent/adoptive parent to complete the study ahead of schedule for any reason.
- 5. Cases not specified by the protocol, when the investigator decides that the further participation may harm the child.
- 6. Incorrect inclusion of ineligible child.
- 7. The patient did not pass the screening procedure.
 - 8. The participant got influenza/ARVI.

Number of subjects

1036 participants of both genders aged 1 month to 6 years old (518 participants in each group) are planned to be included and randomized in the clinical trial. It is estimated that approximately 880 children (440 participants in each group) will complete participation in the study in accordance with the protocol.

Interim analysis

Since the recruitment of participants covers more than one epidemic season, a blind intermediate analysis is carried out in each season (without revealing the participant's membership in one or another experimental group) to possibly clarify a priori research parameters.

Based on the results of a blind interim analysis, a significant difference between the base population frequency of the events studied and the planned one will be revealed, the sample size of the study is reassessed.

Treatment

Group 1

Name of the medicinal product: Anaferon for children

Active ingredient: affinity purified antibodies to human interferon-gamma – 0.003 g*

* applied to lactose monohydrate as water ethanol mixture containing no more than 10^{-16} ng/g of active substance

Excipients: Lactose monohydrate 0.267 g, microcrystalline cellulose 0.03 g, magnesium stearate 0.003 g

Method of administration: Tablet for oral use. One tablet per intake, once daily (approximately at the same time).

The product is administered outside a meal (in the interval between meals or 15 min prior to meal or fluid intake), the tablets should be held in mouth until complete dissolution. For young

children (aged 1 month to 3 years old), the tablet is recommended to be dissolved in a small amount (1 tablespoon) of drinking water of room temperature.

Dosage form: Tablets.

Description: White to off-white, round, flat, scored on one side and beveled tablets. **Storage conditions:** Store at temperature below 25°C. Keep out of the reach of children.

Group 2

Name of the medicinal product: Placebo

Active ingredient: NA

Excipients: Lactose monohydrate 0.267 g, microcrystalline cellulose 0.03 g, magnesium stearate 0.003 g

Method of administration: Placebo using Anaferon for children scheme.

Dosage form: Tablets.

Description: White to off-white, round, flat, scored on one side and beveled tablets.

Storage conditions: Store at temperature below 25°C. Keep out of the reach of children

Treatment duration

Anaferon for children/Placebo treatment duration is 12 weeks.

Observation period

According to the protocol, the child's participation in the study lasts 12 weeks, including screening and randomization (the first day) and the period of study therapy (12 weeks).

Basic therapy

During the entire study period, the participant can receive therapy for the underlying and concomitant diseases that are not criteria for non-inclusion.

Prohibited concomitant therapy

Two weeks prior to enrollment and during the study the following drugs are prohibited:

- 1. Antivirals (J05), except for Anaferon for Children prescribed in this trial.
- 2. Immunostimulants (L03), including:
 - interferon inducers (acridonacetic acid, meglumine acridoacetate/cycloferon[®], umifenovir/arbidol[®], kagocel[®], tilorone/amixin[®], lavomax[®], tilaxin[®], polyadenylic acid + polyuridylic acid/poludan[®], oxodihydroacridinylacetate odium/neovir[®], ribonucleate sodium/ridostin, etc, deoxyribonucleate sodium/derinat[®] etc.)
 - interferons
 - bacterial immunomodulators (including ribomunyl[®], IRS-19, imudon[®],

broncho-munl^{\mathbb{R}} and etc.)

- pidotimod/imunorix
- interleukins
- synthetic immunostimulants (levamisole, alpha-glutamyl-triptophan/thymogen, etc.)
- thymus hormone-containing drugs
- herbal immunostimulants (immunal[®], etc.)
- 3. Immunosuppressants (L04).
- 4. Antineoplastic agents (L01) and hormones (L02).
- 5. Immune sera and immunoglobulins (J06).
- 6. Fenspiride (R03DX03), omalizumab (R03DX05).
- 7. Systemic corticoids (H02AB).
- 8. Homeopathic drugs.
- 9. Drugs known to cause allergic reactions in the patient.

Study design scheme

Schedule of study procedures

| Procedure/visit | Visit 1 | Visit 2 «phone» | Visit 3 «phone» | Visit 4 |
|-----------------------------------|---------|-----------------|-----------------|------------------|
| | (Day 1) | (Week 4±3 days) | (Week 8±3 days) | (Week 12±3 days) |
| Obtaining signed informed consent | + | | | |

CONFIDENTIAL

Protocol No. MMH-AD-008 23-Aug-2018

| | | | | 20 1148 2010 |
|---|---|---|---|--------------|
| form (ICF) | | | | |
| Eligibility assessment | + | | | |
| Recording concomitant medications | + | + | + | + |
| Randomization and prescription of study therapy | + | | | |
| Study drug supply | + | | | |
| Drug accountability and return, assessment of treatment compliance | | | | + |
| Evaluation of treatment safety | + | + | + | + |
| Telephone survey | | + | + | |
| Collection of nasopharyngeal swabs for PCR diagnosis* | | * Performed in case the child falls ill with influenza/ARVI during unscheduled (additional) visit with Visit 4 procedures | | |

Statistical Analysis

Samples

Statistical analysis will be carried out in the following sets:

Total set includes all participants whose parents/adoptive parents signed the Informed Consent Form.

The sample including all enrolled and randomized subjects who received at least one dose of the study drug to be used for analysis of *safety and tolerability* (*Safety population*), as all adverse events identified after the study product administration were recorded.

Full Analysis Set consists of all enrolled and randomized patients, except for those who met at least one of the following criteria:

- 1) failure to meet inclusion/non-inclusion criteria;
- 2) subject failing to take any dose of the study drug;
- 3) absence of any data on the subject after randomization.

This is the best set for the Intention-to-treat method, so it will be used in the Intention-to-treat efficacy analysis of the test therapy.

Per Protocol set. This sample includes all subjects who completed the therapy as per the study protocol, without any missing visits or major protocol deviations. This set will be used in the Per Protocol efficacy analysis of the test therapy.

Evaluation of sample size

The sample size was assessed in accordance with the following rules and assumptions:

- 1. Statistical assumptions:
 - 1.1 the power of statistical tests 'P = (1β) ' is 80% (the probability of correct rejection of the null hypothesis is 0.8)

- 1.2 the probability of type 1 error 'a' is less that 5% (the probability of false acceptance of the alternative hypothesis is less than 0.05);
- 1.3 statistical criteria of intergroup comparisons will be two-sided;
- 1.4 calculation of sample size is based on the assumptions on the expected effect declared in the primary efficacy endpoint;
- 1.5 ratio between Anaferon for children and placebo sample sizes is 1:1 (one Anaferon for children subject: one placebo subject).
- 1.6 statistical hypothesis will be as follows:

null and alternative hypothesis on Anaferon for children superiority using the dosing scheme specified:

in terms of Cox proportional hazard model,

H₀:
$$\ln(T_1/T_2) \le \delta$$

H₁: $\ln(T_1/T_2) > \delta$,

where T_1 – median influenza/ARVI time in Anaferon for children group;

T₂ – median influenza/ARVI time in placebo group;

 Δ , δ –minimum clinically relevant effect.

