1.7 Therefore, sample size will be calculated taking into account

a. Assumption on expected effects declared in the main efficacy criterion;

1.8 calculation of sample size for two-sided test for the final analysis will be made using the formula:

$$n = \frac{\left(z_{\alpha/2} + z_{\beta}\right)^2}{(b - \delta)^2 p_1 p_2 d}$$

where **n** – total sample size of the product and placebo, **p**₁ – proportion of subjects from the total sample size in Anaferon for children group, **p**₂ – proportion of subjects from the total sample size in placebo group, **p**1=**p**2=**0.5**); **b** – effect size (calculated as **b** = **ln**(**T**₁/**T**₂)). δ – minimum clinically relevant effect δ =**ln**(1+ Δ /**T**₂); **z**_{α /2} and **z**_{β} – relevant tabular values of z-test; **d** – expected proportion of subjects reaching primary endpoint during the study.

1.9 Final sample size will be determined using the formula:

$$\mathbf{N}_{\mathrm{F}} = \mathbf{N}_{\mathrm{PP}} / (1 - \mathbf{K}_{\mathrm{B}}),$$

where N_F – final sample size; N_{PP} – result of calculation in cl. 1.8, i.e. scheduled number of children completing the study per protocol; K_B – withdrawal coefficient.

2. Assumptions on expected clinical study effects.

CONFIDENTIAL

It was initially suggested that in Anaferon for children group proportion of subjects falling ill with ARVI/influenza in 12 weeks (84 days) after the treatment onset will not exceed 65%, in placebo group will be at least 80% (conservative estimate based on the study), therefore the difference between the study arms will be less than 15%. Minimum clinically relevant difference between the groups will be 5%.

However, due to essential inability to obtain complete data on all the disease cases in all the subjects enrolled during the study (data censored, right) and necessity to determine typical time to the disease development, we will reformulate the condition on effects in the assumption of exponentially distributed disease cases:

$P_i=1-exp(-\lambda_i T),$

where P_i – proportion of ill subjects in I group, λ_i – risk of disease in I group, T – followup time.

Therefore, evaluation of risk for experimental groups is defined as

$$\lambda_i = \ln(1-P_i)/(-T),$$

median time to the event

$T_{1/2,i}=ln(2)/\lambda_i$

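### The listed criteria let two children of one household be randomised to different arms with look-alike tablets; mixing could dilute the contrast, by an amount the documents do not allow us to estimate.

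*Combined protocol and SAP*

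**What the plan says.** - **Population and unit.** Under Study design and the footnote to inclusion criterion 1, children from 1 month to 6 years 11 months 29 days are eligible, so siblings can qualify together. Each child is randomised individually at Visit 1, in the ratio "one Anaferon for children subject: one placebo subject". The visit may take place at home: "The doctor makes the first visit to the participant in the medical center or at home".
- **Eligibility.** The family-related exclusions concern ties to study staff and to the sponsor. Exclusion 9 begins "The patient's parent/adopter parent is a member of the research team of the investigational site directly involved in the study", and the next item covers sponsor employees. Exclusion 8 covers participation in other trials. No item mentions another child of the household in this trial.
- **Treatment.** Both arms take one tablet daily for 12 weeks. Under Treatment, the Group 1 and Group 2 tablets share one description: "White to off-white, round, flat, scored on one side and beveled tablets".
- **Checks on intake.** Visits 2 and 3 are telephone calls. The schedule of procedures marks drug return and accountability at Visit 4. A child who falls ill in weeks 2 to 12 has a final unscheduled visit with Visit 4 procedures, so the count is made then.
- **Analysis.** The sample size formula (item 1.8) and the listed methods, including PHREG, contain no household term.

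**The concern.** Two siblings in different arms would have two supplies of tablets that look the same, given every day in the same home. If the supplies are mixed, both children receive some of each product and the contrast between them shrinks. A tablet count does not reveal this, because each child still uses one tablet a day and both returns add up.

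The form of the test makes dilution more costly than usual. The null hypothesis is not zero effect but a log ratio of medians of 0.154. The planned effect is about 0.424, so only 0.270 remains to be detected. Any loss is a fraction of 0.424 but is taken out of 0.270. Mixing that has happened cannot be undone in the analysis, and without a household identifier the affected pairs cannot be reliably found.

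**Working it through.** **Inputs from the plan** (Statistical Analysis, Evaluation of sample size, unless stated)

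- Two-sided testing: "statistical criteria of intergroup comparisons will be two-sided", with alpha 0.05 (z = 1.960) and power 80% (z = 0.8416).
- Twelve-week attack rates: active "will not exceed 65%, in placebo group will be at least 80" per cent.
- Median times of 55 days (active), 36 days (placebo) and 42 days (margin). So b = ln(55/36) = 0.424 and δ = ln(42/36) = 0.154. The plan prints ln(56/36) but gives its value as 0.425, which fits 55.
- Event proportion d = 0.725.
- 437 events and 604 per-protocol children in this section; about 880 completers under Number of subjects.

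**Reproducing the plan's figure**

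Events = (1.960 + 0.8416)² / [(b − δ)² × 0.25] = 7.849 / (0.270² × 0.25) = 431. Dividing by 0.725 gives 594 children. The plan has 437 and 604, so its figures reproduce to within 2%.

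**Assumption, not in the documents**

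Let c be the share of all children who are in discordant sibling pairs and whose tablets are fully pooled, so that they contribute no contrast. As an approximation, the average log effect is then b(c) = 0.424 × (1 − c). Independent 1:1 allocation makes about half of sibling pairs discordant. So c = 2%, 5% or 10% needs about 4%, 10% or 20% of children enrolled in sibling pairs, with every discordant pair pooling.

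**Power**

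Power = Φ[(b(c) − 0.154) × √E / 2 − 1.96], evaluated at two event counts:

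- E = 604 × 0.725 ≈ 438, so √E / 2 = 10.46
- E = 880 × 0.725 = 638, so √E / 2 = 12.63

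| c | in sibling pairs | b(c) | b(c) − 0.154 | power, 438 events | power, 638 events |
|---|---|---|---|---|---|
| 0 | – | 0.424 | 0.270 | 81% | 93% |
| 2% | about 4% | 0.416 | 0.262 | 78% | 91% |
| 5% | about 10% | 0.403 | 0.249 | 74% | 88% |
| 10% | about 20% | 0.382 | 0.228 | 66% | 82% |

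**Effect of the margin**

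At c = 10% the detectable difference drops by 0.0424/0.270 = 16%, although b itself drops by only 10%. Against a null of zero with 438 events, the same dilution would take power from 99% to 98%.

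**Milder case**

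Suppose 5% of children are in sibling pairs, so 2.5% are in discordant pairs, and those lose a quarter to a half of the effect. Then b is 0.421 to 0.419, and power at 438 events is 80% to 79%.

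**The case against.** The strongest reply is that nothing here is shown to happen. The documents give no number of siblings, no rate of sharing and no description of packaging or labelling. The text calls itself a protocol summary, so its silence is weaker evidence than silence in a full protocol. That stands, and it is why the figures are a range and not a forecast. The exclusion criteria are nevertheless listed in detail, down to relatives of investigators and of sponsor staff, and households are not among them.

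Other parts of the reply also stand:

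- The look-alike tablets are what blinding requires, and the home visit is incidental; the gap would be the same with clinic visits only.
- Twelve weeks is an upper bound. The plan expects 72.5% of children to fall ill and leave, so in most pairs one child would probably stop early.
- Exclusion 7 lets the investigator turn away families expected not to follow the regimen. That is partial cover, but it does not reach accidental mixing.
- With about 880 completers and d = 0.725, every pooling scenario above stays over 80%. This reserve depends on the event proportion: if 880 completers yielded only 437 events (437/880 = 0.50), it would be gone.

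A reader might infer that sibling enrolment does dilute this trial, that spread of infection between siblings adds to the dilution, or that ignoring their correlation invalidates the Cox analysis. The documents support none of these. With individual 1:1 allocation, correlation lowers the variance of the contrast in discordant pairs and raises it in concordant pairs, and the two roughly offset. Indirect protection narrows the contrast in discordant pairs but can widen it in concordant ones. The net direction is uncertain.

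**Conclusion.** The point holds as an unguarded route to contamination. The listed criteria allow siblings to be randomised to different arms, tablet counts would not detect mixing, and no planned step records it or allows for it. Any mixing within discordant pairs would pull the arms together.

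Its size is unknown. Under the assumptions above, the loss of power runs from about 1 to 2 points (few siblings, partial mixing) to 15 points (about a fifth of children in sibling pairs, complete pooling in every discordant pair) at 438 events, and to 11 points in that same extreme case at 638 events. If few siblings are enrolled, the loss is small. This is a low-cost improvement to the design and not an error in the plan's calculations.

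**What to change.** Add an exclusion criterion: another child of the same household is already enrolled in this trial.

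For sibling pairs already randomised, record a household identifier on the case report form, fit the PHREG model with a household-clustered robust variance, and add a sensitivity analysis that leaves out discordant pairs.

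The cost is one criterion, one form field and a minor addition to a procedure already planned. The downside is that a few eligible siblings are turned away. If the full protocol already has a household rule, stating it in this document is enough.

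### Secondary endpoints 2 and 3 cover the 12-week course, but a child's ARVI visit is final and no record review or contact after it is described

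*Combined protocol and SAP*

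**What the plan says.** All references are to the combined protocol and SAP.

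- **Study design, exit rule.** The rule begins "If in the period from 2 to 12 weeks a participant falls ill", and of such a child it says: "then he prematurely completes participation in the study (as having reached the primary endpoint"). Of the illness visit it says: "the doctor makes an unscheduled visit (at home or in a medical center), which is final".
- **Discontinuation criteria, item 8.** "The participant got influenza/ARVI" is listed with no time limit.
- **Secondary endpoints, items 2 and 3.** Item 2 concerns "bacterial infection requiring antibacterial therapy within 12-week preventive course (based on medical records"). Item 3 concerns "children hospitalized for influenza/ARVI or their complications within 12week preventive course (based on medical records").
- **Study design, telephone visits.** The Week 4 and Week 8 calls ask parents about "possible use of antibacterial drugs and/or hospitalization during the course preventive therapy". Nothing says that they continue for a child who has left.
- **Schedule of study procedures.** The table has Visits 1 to 4 and a note on the swab: "Performed in case the child falls ill with influenza/ARVI during unscheduled (additional) visit with Visit 4 procedures". It has no row for record review and no contact after the illness visit.
- **Evaluation of sample size, point 2.** The plan recognises right-censoring and restates the primary assumption in time-to-event terms. Endpoints 2 and 3 remain percentages. The lists of statistical criteria include both 2×2 tests and survival analysis, without assigning either to these endpoints.

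**The concern.** Endpoint 3 counts admissions that follow an ARVI, and the visit that diagnoses the ARVI is the one that ends observation. Complications and admissions tend to come after that visit, so this endpoint loses most if nothing is collected later. Its rate and event count would be understated in both arms.

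Endpoint 2 mixes infections that follow an ARVI with infections that have nothing to do with it. The unrelated ones are seen only while the child is still in the study, so the arm with more ARVI is watched for less time and loses more of them. With equal visibility by arm, this works against the drug if it prevents ARVI and in its favour if it raises ARVI risk. If the drug has no effect on ARVI, unequal time creates no bias.

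The plan expects 72.5% of children to fall ill, so early exit would be the usual course.

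**Working it through.** **Inputs from the plan.** Evaluation of sample size: P = 80% ill on placebo and 65% on Anaferon by T = 84 days, exponential onset, d = 0.725, 437 events, 604 per-protocol children (302 per group). Number of subjects: 518 per group randomised, about 440 completing.

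**1. Reproducing the plan's figures.** λ = −ln(1−P)/84 gives 0.01916 per day (placebo) and 0.01250 (Anaferon), a hazard ratio of 0.652. The medians ln(2)/λ are 36.2 and 55.5 days (plan: 36 and 55). d = (0.80 + 0.65)/2 = 0.725. Events = (1.960 + 0.842)²/[(0.425 − 0.154)² × 0.25] = 427.5, within 2.2% of the stated 437. None of these figures is disputed here; they set how many children exit and when.

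**2. Time observed if follow-up stops at ARVI.** Mean days = P/λ.
- Placebo: 0.80/0.01916 = 41.8. Share of the window after exit: 1 − 41.75/84 = 50%.
- Anaferon: 0.65/0.01250 = 52.0. Share after exit: 1 − 52.01/84 = 38%.
- Days left per exiting child: (84 − 41.75)/0.80 = 52.8 and (84 − 52.01)/0.65 = 49.2.
- If no child exits in days 1 to 7: 7 + (1 − exp(−77λ))/λ = 47.3 v 56.4 days, so 44% v 33% after exit.

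**3. Lower-rate case (assumption).** If 880 completers were meant to yield the same 437 events, d = 437/880 = 0.497. Keeping the hazard ratio at 0.652, this needs about 57% v 42% ill (λ = 0.01004 and 0.00655). Mean observation is 56.7 v 64.6 days, so 32% v 23% falls after exit.

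**4. Endpoint 2, infections independent of ARVI (assumed 10% in both arms).** h = −ln(0.9)/84 = 0.001254. Proportion seen = h/(h+λ) × [1 − exp(−84(h+λ))].

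| Case | Placebo seen | Anaferon seen | Ratio (true 1.00) |
|---|---|---|---|
| 80% v 65% ill | 5.04% | 6.25% | 1.24 |
| 57% v 42% ill | 6.80% | 7.73% | 1.14 |
| Rates swapped (drug raises ARVI risk) | 6.25% | 5.04% | 0.81 |

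Assumed backgrounds of 2% and 5% also give about 1.24 in the first case. With no exits in days 1 to 7 it is 1.19. For the first row, z = 0.64 at 302 per arm, 0.78 at 440 and 0.84 at 518, all well below 1.96.

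**5. Endpoint 2, mixed (assumed 5% background plus 5% of ARVI cases; 80% v 65% ill).** True: 5% + 0.05P = 9.0% v 8.25%, ratio 0.917. Background seen before exit: 2.50% v 3.11%. If half of the ARVI-linked infections are visible by the final visit, 4.50% v 4.73% is seen, ratio 1.052, a distortion of 1.052/0.917 = +15%. If all are visible, 6.50% v 6.36% is seen, a distortion of +7%.

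**6. Endpoint 3 (assumed 5% of ARVI cases admitted).** True: 0.05 × 0.80 = 4.0% v 0.05 × 0.65 = 3.25%, ratio 0.81. If half are visible by the final visit, 2.0% v 1.625% is seen. At 302 per arm, 12.1 v 9.8 admissions become 6.0 v 4.9. The ratio stays at 0.81 only if visibility is equal; 50% (placebo) v 60% (Anaferon) visible gives 0.98, and 50% v 40% gives 0.65. Two-sided power falls from about 8% to 6% at 302 per arm and from 9% to 7% at 440.

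**7. Does dividing by time at risk help?** Not for endpoint 3. With half visible, (1.625%/52.0 days)/(2.0%/41.75 days) = 0.65 against a risk ratio of 0.81. ARVI ends the time at risk just as the risk of admission begins, so the apparent benefit grows.

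**The case against.** Both endpoints name medical records as their source, and records do not depend on study visits. The file is also a protocol summary, so silence about who reads the records and when is weak evidence that nobody will. This stands against one stronger reading: a reader might infer that later events have no possible route into the data. The documents do not support that. They name a source, and they leave open whether it is read beyond the exit visit and how children who have left enter the percentages. Events up to that visit can be captured, because Visit 4 procedures are done there.

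The preventive course could also be read as ending with the child's own exit, which is a legitimate window. The plan does not say so. Under that reading, endpoint 2 still rests on unequal observation by arm, and endpoint 3 excludes most of what follows the illness.

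Finally, the practical weight is modest. Every event rate and visible share for endpoints 2 and 3 is assumed, and endpoint 3 has little power even with full capture. That is correct, and it is why this is a low-cost improvement and not a threat to the trial.

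**Conclusion.** The point holds as an undescribed procedure. The exit rule and the 12-week window do not fit together unless records are read, or contact is kept, after the ARVI visit. If neither is done, endpoint 3 is understated in both arms and endpoint 2 loses more unrelated infections in the arm with more ARVI.

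The share of the window at stake is about 50% v 38% at the plan's own rates, or about 32% v 23% in the lower-rate case. The matching 24% and 14% distortions of the endpoint 2 risk ratio assume that every infection is unrelated to ARVI; ARVI-linked infections that are visible by the final visit reduce them. These are illustrations, not bounds.

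Two further inferences go too far. One is that the bias can only hurt the drug: that needs a drug that does not raise ARVI risk and equal visibility by arm, and the documents guarantee neither. The other is that the gap could by itself produce a significant result or reach the main comparison. In the 10% illustration z is at most 0.84 at 302 to 518 per arm, and the primary endpoint and secondary endpoint 1 are settled by the ARVI itself.

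**What to change.** This concerns data collection only; treatment rules stay as they are.

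- State that medical records are reviewed to Day 84 for every randomised child, or that the already scheduled Week 4, 8 and 12 contacts continue by telephone after ARVI.
- Analyse endpoints 2 and 3 as percentages of all randomised children over that window, and state that it includes time off treatment.
- Reconcile the final-visit wording in Study design, Discontinuation criteria item 8 and the missing-visits condition of the Per Protocol set with this follow-up.
- Do not use a time-at-risk analysis censored at ARVI for endpoint 3 or for ARVI-linked infections.
- If follow-up cannot be extended, relabel both endpoints as events up to the final visit and report them as such.

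The cost is a sentence or two of protocol text with matching edits, some call or record-review time, some loss to follow-up after ARVI, and an off-treatment portion in the window (larger on placebo if the drug works). The primary endpoint and its sample-size calculation do not change.
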